## 8. BIOSPECIMEN STUDIES AND PROCEDURES

While anti-PD-1/L1 improves clinical outcomes for patients with many cancers, it appears that these responses are best in tumors with dense lymphocytic infiltration or PD-L1 positivity, arguing that improved outcome is associated with a pre-existing anti-cancer immune response (59). Based on this, we hypothesize that strategies which can convert “cold” tumors, lacking T cell infiltrates and PD-L1+ cells, into “hot” tumors with brisk T cell infiltrates, will increase response rate and overall survival.

This proposal seeks to perform Multiplex immunohistochemistry (mIHC) on pre-treatment biopsies of patients enrolled on this clinical trial. This will help us identify patients whose pretreatment tumors lack TIL and/or PD-L1+ cells and determine whether the tumor micro environment (TME) may be associated with clinical outcomes. Our group has applied mIHC to develop a next generation of immunoscore, termed the cumulative suppressive index (CSI). The CSI incorporates PD-L1 and FoxP3+ cells as well as their respective distance to CD8 T cells to provide a prognostic biomarker (10). We are currently evaluating whether it can also serve as a predictive biomarker. Recently, a similar approach has used distance measurements to evaluate PD-1+ cells in close proximity to PD-L1+ cells and showed a significant correlation with response to checkpoint blockade (11). The same report also identified that close proximity of IDO and HLA-DR expression was also predictive of increased overall survival. Patients positive for both multiplex IHC assessments had a significantly ( $P=0.0018$ ) improved overall survival. We posit that these two predictive biomarkers represent a surrogate of a T cell immune response to the patient’s cancer. Supporting this concept, a retrospective analysis of five clinical trials found that multiplex IHC was a better than gene expression profiling, tumor mutational burden or PD-L1 expression at predicting response to checkpoint blockade (12). On this basis we propose performing the CSI, as well as the PD-1/PD-L1 and IDO/HLA-DR proximity assays on biopsy samples from patients enrolled on this study.

Samples for immunological monitoring will include blood (including for circulating tumor DNA analysis), archival tumor tissue, and collecting peripheral blood mononuclear cells (PBMC) and serum. The main objectives of the monitoring will be to characterize circulating T-cell subsets and changes in the tumor microenvironment (TME) following treatment that may correlate with clinical responses.

Flow cytometry analysis with a panel of markers including CD3, CD4, CD8, CD25, CD127, CCR7, FoxP3, ICOS, and CD45RA will be performed. T cell sub-populations of interest include effector, regulatory T cell ( $T_{reg}$ ), central memory, and effector memory cells. Other immunological measures may be evaluated including, but not limited to, immunohistochemistry analysis of biopsy samples and measurement of serum cytokine levels using multiplex ELISA (Luminex assay) to generate hypotheses for future studies and to gain insight into possible biomarkers of response.

### 8.1 Tissue

### 8.1.1 Archival Tissue

Archival tissue is required if available and may be submitted for PD-L1 testing (if not performed by 22C3 or SP263 assay at treating institution per standard of care). Tissue should be identified at screening and shipped prior to chemoradiation. Testing for tumor mutation burden will be performed. TMB is calculated as the number of somatic mutations per megabase of DNA across a 500-gene panel. Archival tissue will be stored for future multispectral immunohistochemistry evaluation. Analysis to be performed pending the availability of funding.

## 8.2 Peripheral Blood Samples

Analysis to be performed pending the availability of funding.

### 8.2.1 Serum

Specimens for serum will be collected prior to C1D1 induction durvalumab; prior to C1D1 consolidation durvalumab; and at 8 weeks after consolidation durvalumab (prior to Cycle 3) for immune monitoring analysis. All specimens should be collected prior to drug administration.

### 8.2.2 Peripheral Blood Mononuclear Cells (PBMCs)

Specimens for PBMCs will be collected prior to C1D1 induction durvalumab; prior to C1D1 consolidation durvalumab; and at 8 weeks after consolidation durvalumab (prior to Cycle 3) for immune monitoring analysis. All specimens should be collected prior to drug administration.

### 8.2.3 ctDNA

Specimens will be collected prior to C1D1 induction durvalumab; prior to C1D1 consolidation durvalumab; and at 8 weeks after consolidation durvalumab (prior to Cycle 3) for circulating tumor DNA analysis.

## 8.3 Microbiome

Microbiome stool specimens will be collected from each patient at screening or prior to C1D1 of induction durvalumab. Analysis to be performed pending the availability of funding.

## 8.4 Banking of Leftover Biospecimens

Subject consent will be obtained to bank any leftover samples collected for study-specific correlative research prior to C1D1 treatment. Hoosier Cancer Research Network (HCRN) will manage the banked samples. Samples will be banked indefinitely in the Hoosier Cancer Research Network Biorepository and used for future unspecified cancer-related research.

Please refer to the Correlative Laboratory Manual (CLM) for all sample collection, processing, labeling, and shipping instructions.

## 8.5 Confidentiality of Biospecimens

Samples that are collected will be identified by a subject's sequence ID assigned at the time of registration to the trial. Any material issued to collaborating researchers will be anonymized and only identified by the subject's study number.

reference to further characterize any objective tumor regression in the measurable dimension of the disease.

#### 9.4 Non-target Lesions

All other lesions (or sites of disease) including any measurable lesions over and above the 5 target lesions should be identified as non-target lesions and should also be recorded at baseline. Measurements of these lesions are not required, but the presence, absence, or in rare cases unequivocal progression of each should be noted throughout follow-up.

#### 9.5 Evaluation of Target Lesions

NOTE: In addition to the information below, also see the international criteria proposed by the Response Evaluation Criteria in Solid Tumors (RECIST) Committee, version 1.1 (Eur J Cancer 45;2009:228-247) for special notes on the assessment of target lesions.

Complete Response (CR)	Disappearance of all target lesions. Any pathological lymph nodes (whether target or non-target) must have reduction in short axis to <10 mm.
Partial Response (PR)	At least a 30% decrease in the sum of the diameters of target lesions, taking as reference the baseline sum diameters
Progressive Disease (PD)	At least a 20% increase in the sum of the diameters of target lesions, taking as reference the smallest sum on study (this includes the baseline sum if that is the smallest on study). In addition to the relative increase of 20%, the sum must also demonstrate an absolute increase of at least 5 mm. (Note: the appearance of one or more new lesions is also considered progressions).
Stable Disease (SD)	Neither sufficient shrinkage to qualify for PR nor sufficient increase to qualify for PD, taking as reference the smallest sum diameters while on study

#### 9.6 Evaluation of Non-Target Lesions

Complete Response (CR)	Disappearance of all non-target lesions and normalization of tumor marker level. All lymph nodes must be nonpathological in size (<10 mm short axis)  NOTE: If tumor markers are initially above the upper normal limit, they must normalize for a subject to be considered in complete clinical response.
Non-CR/ Non-PD	Persistence of one or more non-target lesion(s) and/or maintenance of tumor marker level above the normal limits

Progressive Disease (PD)	Appearance of one or more new lesions and/or unequivocal progression of existing non-target lesions. Unequivocal progression should not normally trump target lesion status. It must be representative of overall disease status change, not a single lesion increase.
--------------------------	--

Although a clear progression of “non-target” lesions only is exceptional, the opinion of the site investigator should prevail in such circumstances, and the progression status should be confirmed at a later time by the sponsor investigator.

## 9.7 Evaluation of Best Overall Response

Target Lesions	Non-Target Lesions	New Lesions	Overall Response
CR	CR	No	CR
CR	Non-CR/ Non-PD	No	PR
CR	Not evaluated	No	PR
PR	Non-PD/ or not all evaluated	No	PR
SD	Non-PD or not all evaluated	No	SD
Not all evaluated	Non-PD	No	Non-evaluable
PD	Any	Yes or No	PD
Any	PD*	Yes or No	PD
Any	Any	Yes	PD

\*In exceptional circumstances, unequivocal progression in non-target lesions may be accepted as disease progression.

Subjects with a global deterioration of health status requiring discontinuation of treatment without objective evidence of disease progression at that time should be classified as having “symptomatic deterioration.” Every effort should be made to document the objective progression even after discontinuation of treatment.

In some circumstances, it may be difficult to distinguish residual disease from normal tissue. When the evaluation of complete response depends on this determination, it is recommended that the residual lesion be investigated (fine needle aspirate/biopsy) to confirm the complete response status.

## 9.8 Definitions for Response Evaluation – RECIST 1.1

### 9.8.1 First Documentation of Response

The time between initiation of therapy and first documentation of PR or CR.

#### 9.8.2 Confirmation of Response

To be assigned a status of complete or partial response, changes in tumor measurements must be confirmed by repeat assessments performed no less than four weeks after the criteria for response are first met.

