## 2.2 Endpoints

### 2.2.1 Primary Endpoints

- 12-month progression-free survival will be measured using imaging after completion of chemoradiation, prior to C1 consolidation durvalumab (1-42 days after completion of chemoradiation). This will be compared with PACIFIC trial 12-month progression-free survival as historical control.
- Toxicity will be measured by the NCI Common Terminology Criteria for Adverse Events (NCI CTCAE) v5.

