### 2.2.2 Secondary Endpoints

- Objective response rate (ORR). ORR will be measured using two timepoints, per RECIST 1.1. “ORR1” will be assessed using baseline imaging in comparison to imaging obtained after completion of induction durvalumab and chemoradiation. “ORR2” will be assessed using imaging after completion of induction durvalumab and chemoradiation in comparison to imaging obtained while receiving, and after completion of, consolidation durvalumab.

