### 5. TREATMENT PLAN

This is a single arm study of induction durvalumab at 1500 mg intravenously (IV) on Day 1 of a four week cycle for 1 cycle, followed by concurrent definitive chemoradiation, followed by consolidation durvalumab at 1500 mg IV Day 1 of every 4 week cycle for up to 12 cycles.

Chemoradiation should begin no earlier than 4 weeks and no later than 5 weeks after the dose of induction durvalumab. Patients meeting required criteria for consolidation and without disease progression after chemoradiation should begin consolidation durvalumab within 1-42 days after

completion of chemoradiation. Subjects unable to start within the timeframes described should be discussed with the sponsor-investigator. Concurrent chemoradiation will be with platinumbased chemotherapy (cisplatin or carboplatin, with etoposide, taxane, or pemetrexed) selected at the treating physician's discretion. Patients receiving different chemotherapeutic agents will be analyzed together for toxicity, with exploratory analysis of toxicity related to different chemotherapeutic regimens. Radiation will be administered using standard fractionation at a dose of 54-66 Gy.

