4: Vital signs to include temperature, pulse, respirations, blood pressure, weight, and height (screening only) and ECOG performance status. Patients will be monitored before, during and after the durvalumab infusion with assessment of vital signs. Patients are monitored (pulse rate, blood pressure) every 30 minutes (- 5 minutes/+ 10 minutes), during the infusion period (including times where infusion rate is slowed or temporarily stopped).

5: CBC with differential and platelet to include: WBC, ANC, Hgb, Hct, PLT. CMP to include sodium, potassium, chloride, creatinine, blood urea nitrogen; liver function tests (LFTs) to include AST, ALT, total bilirubin, alkaline phosphatase. Thyroid Function testing should be performed at

screening, at start of consolidation durvalumab, then every 3 cycles during consolidation durvalumab. TSH will be obtained. T4 and T3 including free versus total testing is at the discretion of the site investigator.

6: For women of childbearing potential (WOCBP): urine or serum  $\beta$ hCG will be done at screening and within 24 hrs of 1st dose of study drug. During treatment with consolidation durvalumab, a pregnancy test should be performed every 4 weeks. If a urine test is done and it is positive or cannot be confirmed as negative, a serum pregnancy test will be required.

7: Tumor assessments to be performed at (1) screening (PET scan may be within 42 days prior to C1D1) (2) within 0-24 days after completion of chemoradiation/prior to C1D1 of consolidation durvalumab, then every 3 months (about every 3 cycles/ $\pm$  7 business days) during consolidation durvalumab. Screening tumor assessment will consist of evaluation by CT scans of chest (contrast enhanced), PET scan, and contrast-enhanced MRI or CT of the brain. Response assessment imaging will include CT scans of chest, abdomen, and pelvis (contrast enhanced). MRI or CT brain or PET scan after screening should be performed as clinically indicated. Imaging selected for each subject should remain the same throughout the study. Tumor imaging at treatment discontinuation/D30 safety follow up visit is at discretion of site investigator. If tumor assessments are available for subjects who have not yet experienced progressive disease (PD) at the time treatment is discontinued, the follow-up tumor evaluations will be documented in the eCRF until PD or death is confirmed, or until another treatment is initiated. A window of 7 days may be applied to obtain scans.

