12: After the D100 safety visit, subjects who discontinue treatment for any reason without documented disease progression will be followed for disease progression every 3 months up to 12 months after initiation of consolidation durvalumab. Once disease progression is documented, subjects will enter a survival follow up period every 6 months for 1 year from the time of documented progression or until 1 year after initiation of consolidation durvalumab. Follow up may be accomplished via clinic visit, phone call, or other avenues as appropriate. A window of  $\pm$  14 days will be applied to follow up.

13: If screening (baseline) CBC and CMP were performed within 7 days of Day 1 of treatment, these do not need to be repeated. All laboratory assessments should be done prior to treatment.

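### Section 9.8.2 requires every response to be confirmed, but no scheduled scan can confirm an ORR1 response before consolidation starts

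*Combined protocol and SAP*

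**What the plan says.** Section 9.8.2 is mandatory and names no exception: a tumour change counts as CR or PR only if it "must be confirmed by repeat assessments performed no less than four weeks after the criteria for response are first met".

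Section 2.2.2 says that ORR1 "will be assessed using baseline imaging in comparison to imaging obtained after completion of induction durvalumab and chemoradiation". Sections 9.8.5 and 12.2.2 make the same comparison. None of the three mentions confirmation. Section 9.8.5 stands under the same heading (9.8, RECIST 1.1 definitions) as the confirmation rule.

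The study calendar (section 7) marks no tumour imaging during induction or chemoradiation. After screening, footnote 7 asks for an assessment "within 0-24 days after completion of chemoradiation/prior to C1D1 of consolidation durvalumab, then every 3 months" during consolidation. Section 5 says that eligible patients "should begin consolidation durvalumab within 1-42 days after" the end of chemoradiation, and it describes "consolidation durvalumab at 1500 mg IV Day 1 of every 4 week cycle for up to 12 cycles".

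For patients off treatment, footnote 7 says "Tumor imaging at treatment discontinuation/D30 safety follow up visit is at discretion of site investigator". Footnote 12 says that "subjects who discontinue treatment for any reason without documented disease progression will be followed for disease progression every 3 months up to 12 months", counted from the start of consolidation. This follow-up begins once the day-100 visit has passed, and contact may be by telephone.

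Section 12.6.2 compares ORR between the two time points, with McNemar's test for paired data. It does not say whether confirmed or unconfirmed responses are used.

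**The concern.** The post-chemoradiation scan is the first scheduled scan at which a response can be seen, and the only one before consolidation. The plan therefore demands a confirmation that its own calendar does not provide within the phase that ORR1 describes.

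ORR is the only secondary objective. ORR1 is the only efficacy endpoint confined to induction plus chemoradiation, because PFS is measured from after chemoradiation. Two analysts could both follow the text and report different ORR1 values: one using the single scan, the other crediting only responses still present three months into consolidation. If that choice is made after the data are seen, it is a post-hoc choice.

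**Working it through.** The documents give no target, expected rate or power for ORR1, so there is no stated figure to reproduce. The check is one of timing.

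**Step 1. Could a repeat scan fit before consolidation?** Let *s* be the scan day and *c* the consolidation start day, both counted from the end of chemoradiation, with *s* ≤ *c*. Confirmation on or before C1D1 needs *c* − *s* ≥ 28.

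*Calendar window:* *s* = 0 to 24 (footnote 7), *c* = 1 to 42 (section 5).
- Admissible pairs: 42 for *s* = 0, plus the sum of (43 − *s*) for *s* = 1 to 24, which is 24 × 43 − 300 = 732. Total 42 + 732 = 774.
- Pairs with room for a repeat: 15 for *s* = 0, 14 for *s* = 1, and so on down to 1 for *s* = 14. Total 15 × 16 / 2 = 120.
- Share: 120 / 774 = 15.5%. The largest gap is 42 − 0 = 42 days. It works only if the scan is by day 14 and consolidation starts on day 28 or later.

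*Endpoint-text window:* section 2.2.1 places the imaging "prior to C1 consolidation durvalumab (1-42 days after completion of chemoradiation"), so *s* = 1 to 42.
- Admissible pairs: 42 × 43 / 2 = 903.
- Pairs with room: 14 + 13 + … + 1 = 105.
- Share: 105 / 903 = 11.6%. The largest gap is 42 − 1 = 41 days.

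These are shares of calendar combinations, not of patients. Even where a repeat fits, none is scheduled.

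**Step 2. When is the next scheduled scan, and how much consolidation drug precedes it?** Three cycles are 3 × 28 = 84 days and three months about 91 days. The window is ±7 business days, taken here as 9 to 11 calendar days. Doses fall on days 0, 28, 56 and 84 from C1D1.
- Early end: 84 − 11 = day 73, after 3 doses.
- Nominal three cycles: day 84, after 3 doses.
- Nominal three months: day 91, after 4 doses.

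This scan meets the four-week rule, but only on consolidation durvalumab.

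**Step 3. What else does that scan feed?** Section 2.2.2 defines ORR2 on imaging both during and after consolidation, so the month-3 scan counts toward ORR2. It would then help decide both sides of the paired comparison in 12.6.2. Sections 9.8.5 and 12.2.2 define ORR2 on imaging after consolidation only. Under those, the overlap disappears, but ORR1 still depends on consolidation.

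**Step 4. Patients who never start consolidation.** Section 3.3 bars some patients, for example for pneumonitis of any grade. They have no on-consolidation scans, their imaging at discontinuation is discretionary, and the footnote 12 follow-up limit is dated from a consolidation start that they do not have.

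**The case against.** The strongest reply is that ORR1 is defined three times as a comparison of two scans, with no mention of confirmation, while 9.8.2 is a general definition that does not name ORR1. If the specific text governs, ORR1 is simply unconfirmed. That is a plausible reading, but 9.8.2 has no exemption and sits beside 9.8.5 under one heading, so this reading contradicts a stated rule. The conflict has to be settled in the text.

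Three stronger claims that a reader might infer do not hold:
- *That confirmation before consolidation is impossible.* The windows allow up to 41 or 42 days between scan and C1D1, and section 5 lets starts outside the window be discussed with the sponsor-investigator. The repeat is unscheduled, not impossible.
- *That ORR1 must be either zero or dependent on consolidation.* Those are the outcomes of applying 9.8.2 on scheduled scans. The unconfirmed reading is a third possibility.
- *That patients who never start consolidation can never be confirmed.* The calendar marks CT in the follow-up columns, and footnote 7 records follow-up evaluations where available. Some could be confirmed, but not reliably.

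It is also fair that ORR1 carries no decision rule, plays no part in the sample size, and cannot separate induction from chemoradiation, because no scan lies between them.

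**Conclusion.** The point holds as a conflict between 9.8.2 on one side and the ORR1 definition and calendar on the other. It should be corrected, but it does not touch the primary analysis.

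The conclusion rests on the scheduled scans only, and on 9.8.2 applying to ORR1 as its wording and position imply. The dose count assumes that cycles run to schedule.

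The size of the effect on ORR1 cannot be derived from the documents. A reader might try to compute it. With an assumed 60% response, 90% starting consolidation, and 90% or 70% of responders still confirmed at month 3, the result is 0.60 × 0.90 × 0.90 = 48.6% or 0.60 × 0.90 × 0.70 = 37.8%, about 11 to 22 points lower. The documents do not support this. The 60% and the 90% or 70% have no source in them, and the 10% in section 12.3 is a dropout allowance for sample size, not a rate of never starting consolidation. Nor is the gap simply bias, since confirmed response is a stricter measure than unconfirmed response.

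**What to change.** - In 9.8.2 and 9.8.5, state that the confirmation rule does not apply to ORR1, which is the single post-chemoradiation scan against baseline and is reported as unconfirmed.
- In 12.6.2, use the same unconfirmed response definition for ORR1 and ORR2. Confirming ORR2 alone would make part of any difference a matter of definition.
- Report confirmed ORR2 separately, for patients with a later scheduled scan. A response first seen at the end of consolidation may have none, because footnote 12 ends progression follow-up 12 months after consolidation starts.
- Reconcile the ORR2 imaging period (2.2.2 against 9.8.5 and 12.2.2) and the post-chemoradiation imaging window (0 to 24 days in footnote 7; 1 to 42 days in 2.2.1, 9.8.8 and 12.2.1).

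The cost is wording: no added scans, visits or patients. The small downside is that ORR1 carries the label unconfirmed. The text should be settled before ORR is analysed.

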#### 9.8.3 Duration of Response

Duration of overall response—the period measured from the time that measurement criteria are met for complete or partial response (whichever status is recorded first) until the date that recurrent or progressive disease is objectively documented (taking as reference for progressive disease the smallest measurements recorded since treatment started).

